7.4. Pharmacokinetic Sampling

7.4.1. PK Sampling Time Points for All Subjects

Blood samples for PK analyses of tofacitinib will be collected from all subjects at Month 12, Month 24, Month 36 visits, and/or at the End of Study/Early Termination (if feasible) up to Month 36. While PK sampling is desired at the End of Study/Early Termination visit (up to Month 36), it is recognized that this collection may not be possible or feasible if drug has been discontinued prior to this visit; a comment should be included in the applicable PK CRF page.

PK samples should be obtained pre-dose and post-dose at 0.5 hr (time window: 0.25-0.75 hr), and 2hr (time window: 1.75-2.5 hr) after the dose is given at the study site.

Before the visits where a pre-dose PK sample is collected, the subject and parent/legal guardian will be instructed that the subject should not take the morning dose of study medication on the visit day until after the pre-dose PK sample is collected.

Note: PK samples will not be collected from subjects participating at India sites.

7.4.2. Plasma for Analysis of Tofacitinib

Blood samples (1.2 mL) to provide a minimum of 0.6 mL of plasma for PK will be collected into appropriately labeled tubes containing lithium heparin.

The actual times may change but the number of samples will remain the same. All efforts will be made to obtain the PK samples at the exact nominal time relative to dosing. However, samples obtained within the specified time window will not be captured as a protocol deviation, as long as the exact time of the sample collection is noted on the source document and data collection tool (eg, CRF).

Samples will be centrifuged at approximately 1700 g for about 10 minutes at 4°C. The plasma will be stored in appropriately labeled screw-capped polypropylene tubes at approximately -20°C within 1 hour of collection.

Samples will be analyzed using a validated analytical method in compliance with Pfizer standard operating procedures.

7.4.3. Shipment of Pharmacokinetic Samples

The shipment address and assay lab contact information will be provided to the investigator site prior to initiation of the study.

8. ADVERSE EVENT REPORTING

8.1. Adverse Events

All observed or volunteered AEs regardless of treatment group or suspected causal relationship to the investigational product(s) will be reported as described in the following sections.

For all AEs, the investigator must pursue and obtain information adequate both to determine the outcome of the AE and to assess whether it meets the criteria for classification as a serious adverse event (SAE) requiring immediate notification to Pfizer or its designated representative. For all AEs, sufficient information should be obtained by the investigator to determine the causality of the AE. The investigator is required to assess causality. Follow-up by the investigator may be required until the event or its sequelae resolve or stabilize at a level acceptable to the investigator, and Pfizer concurs with that assessment.

As part of ongoing safety reviews conducted by the Sponsor, any non-serious adverse event that is determined by the Sponsor to be serious will be reported by the Sponsor as an SAE. To assist in the determination of case seriousness further information may be requested from the investigator to provide clarity and understanding of the event in the context of the clinical study.

8.2. Time Period and Frequency for collecting AE and SAE Information

The time period for actively eliciting and collecting AEs and SAEs (“active collection period”) for each participant begins from the time the participant provides informed consent, which is obtained before the participant’s participation in the study (ie, before undergoing any study-related procedure and/or receiving study intervention), through and including a minimum of 28 calendar days after the last administration of the study intervention or until study completion or withdrawal, whichever is longer.

Follow-up by the investigator continues throughout and after the active collection period and until the AE or SAE or its sequelae resolve or stabilize at a level acceptable to the investigator and Pfizer concurs with that assessment.

For participants who are screen failures, the active collection period ends when screen failure status is determined.

If the participant withdraws from the study and also withdraws consent for the collection of future information, the active collection period ends when consent is withdrawn.

If a participant definitively discontinues or temporarily discontinues study intervention because of an AE or SAE, the AE or SAE must be recorded on the CRF and the SAE reported using the CT SAE Report Form.

Investigators are not obligated to actively seek AEs or SAEs after the participant has concluded study participation. However, if the investigator learns of any SAE, including a death, at any time after a participant has completed the study, and he/she considers the event

to be reasonably related to the study intervention, the investigator must promptly report the SAE to Pfizer using the CT SAE Report Form.

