Depending on local regulatory requirements, and as per the EU Voluntary Harmonisation Procedure (EU VHP), access to tofacitinib may be made available to patients after the conclusion of this study via, but not limited to, an expanded access/compassionate use program until either 1) commercially available for JIA; 2) no longer beneficial to a patient as determined by the treating investigator; 3) the benefit-risk for JIA is determined to be unfavorable; or 4) the sponsor's application for marketing authorization is denied/disapproved for any reason by both US Food And Drug Administration (FDA) and European Medicines Agency (EMA).

The Sponsor may continue to provide tofacitinib to patients benefitting from this treatment in situations where the patient cannot access treatment through typical post-approval channels. Availability of the oral solution formulation may be limited or discontinued when patients taking the oral solution have either discontinued treatment or have transitioned to use of the oral tablet formulation consistent with applicable weight based dosing guidance.

SCHEDULE OF ACTIVITIES

The Schedule of Activities table provides an overview of the protocol visits and procedures. Refer to Study Procedures ([Section 6](#)) and Assessments ([Section 7](#)) for detailed information on each procedure and assessment required for compliance with the protocol.

The Investigator may schedule visits (unplanned visits) in addition to those listed on the Schedule of Activities, in order to conduct evaluations or assessments required to protect the well-being of the subject.

For Investigative Sites in Belgium Only: The degree of burden and the risk threshold should be assessed at each scheduled visit as outlined in [Appendix 13](#).

For any visits impacted by public emergencies, including the COVID-19 pandemic, refer to [Appendix 14](#) for additional guidance and instructions.

Protocol Activity	Subjects >14 days after EOS ⁷ Visit		Combined with EOS ⁷ Visit	Separate Visit within 14 days after EOS ⁷ Visit	Year 1 Months 1, 3, 6, 9, 12 ⁸	Years 2-5 Every 3 Months ⁸	Years 6-10 Every 3 months (except at Months 72, 84, 96, 108, 120) ⁸	Years 6-10 Months 72, 84, 96, 108, 120 ⁸	End of Study /Early Termination
	Screening	Baseline	Screening /Baseline	Screening /Baseline					
Informed Consent/Assent	X		X	X					
Medical History	X								
Adverse Events (AE) assessment	X ^d	X ^d	X ^d	X ^d	X	X	X	X	X

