- Tanner stage is performed at Baseline Visit and annually thereafter. No need to be repeated after the subject has reached Tanner Stage 5.
- Uveitis Exam by an ophthalmologist (or qualified equivalent per local practice) is performed at Screening (if no exam is done within past 6 months), then annually thereafter, and at End of study/Early Termination Visit. If the exam was performed within the past 6 months the next uveitis exam should occur 1 year after the previous exam and annually thereafter. The window for this particular examination is ± 30 days relative to the visits where uveitis exam is performed (see Section 6.2 and Section 6.2.5 for additional details). At all other visits the investigator should assess if there are potential changes in uveitis status and refer for formal evaluation if deemed clinically necessary. For JIA subtypes that may require more frequent uveitis examination, investigators should manage this type of examination according to local standard of care. For subjects with sJIA, this exam is not required but if available, documentation of previous uveitis assessment(s) by an ophthalmologist (or qualified equivalent per local practice) should be reviewed, the date of the prior examination recorded, and the presence/absence of active uveitis documented.
- Serious adverse events (SAEs) are captured from the time of informed consent at Screening. For more information see Section 7.2.5. Adverse events (AEs) are captured following the first dose of investigational product.
- The contraception check is an opportunity to confirm that contraception is used consistently and correctly. Also, it is the opportunity to assess changing potential to father/bear children and allows for implementing contraception and pregnancy testing as children mature physically and behaviorally during conduct of the study.

TABLE OF CONTENTS

PROTOCOL SUMMARY	7
SCHEDULE OF ACTIVITIES.....	11
LIST OF TABLES	21
LIST OF FIGURES	21
APPENDICES	22
1. INTRODUCTION	23
1.1. Indication.....	23
1.2. Background	23
1.2.1. Study Rationale.....	23
1.2.2. Dose Rationale.....	24
1.2.3. Single Reference Safety Document	26
2. STUDY OBJECTIVES AND ENDPOINTS.....	26
2.1. Objectives.....	26
2.1.1. Primary	26
2.1.2. Secondary	26
2.1.3. Exploratory	26
2.2. Endpoints.....	27
2.2.1. Primary	27
2.2.2. Secondary	27
2.2.3. Exploratory	28
2.3. Benefit/Risk Assessment.....	28
2.3.1. Risk Assessment	28
2.3.2. Benefit Assessment.....	29
2.3.3. Overall Benefit/Risk Conclusion.....	30

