6.2.5. End of Study Visit/Early Termination Visit

The following procedures and assessments will be performed:

- AE assessment.
- Risk factor check for venous thromboembolism (see [Section 7.2.10](#)).
- Document concomitant medications (ongoing or started since previous visit).
- Childhood Health Assessment Questionnaire (CHAQ).
- Vital signs: temperature (oral, tympanic or temporal preferred), BP and PR. For subjects with sJIA: temperature must be measured orally using a digital thermometer, with the exception of very young children or others who cannot tolerate an oral thermometer. In these cases temperature may be measured rectally using a digital thermometer. The definition of fever with a rectal thermometer is one degree Fahrenheit higher. (Example >101.4°F/38.6°C rectally compared to >100.4°F/38°C orally).

Complete physical examination. (**Applicable to Investigative Sites in the UK and Belgium:** a full skin cancer examination must be performed as part of the complete physical examination. **Applicable to subjects enrolled from Study A3921165:** a skin examination for chicken pox or shingles must be performed).

- Tanner stage assessment.
- Physician global evaluation of disease activity.
- Joint assessment of active arthritis (swelling, pain/tenderness), and limitation of motion.
- Duration of morning stiffness.
- Safety laboratory testing (chemistry, hematology, urinalysis), including urine pregnancy testing (β -hCG) for females of child-bearing potential.
- Confirm highly effective contraception is being used.
- Please note: Subjects must use contraception consistently and correctly for at least 28 days after the last dose of investigational product.
- Lipid panel (cholesterol, indirect LDL, direct HDL, apolipoprotein A-1 and B, triglycerides).

***** Important Note ** Subjects should be instructed to fast (for 9 to 12 hours prior the scheduled visit), if possible, for lipid panel testing.***

- CRP.
- Erythrocyte sedimentation rate (ESR) determination (Westergren method).
- PK blood samples (pre-dose, and post-dose at 0.5 hr [time window: 0.25-0.75 hr] and 2 hr [time window: 1.75-2.5 hr] if early termination occurs within 36 months).

***** Important Note ** Subject and parent/legal guardian should be instructed that the subject should NOT take the morning dose at home. The subject's morning dose will be taken at the study site after pre-dose PK sampling.***

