- Components: cardiovascular death, non-fatal myocardial infarction, and non-fatal stroke.
- Including SMQs: Hepatic failure, fibrosis, and cirrhosis, and other liver damage-related conditions; and Hepatitis, non-infectious.
- Including Acute renal failure SMQ.
- Adjudicated by an internal review committee.

Incidence Rates (IRs) will be calculated and presented in 100 subject-years and defined as follows:

$$\text{IR} = 100 * \frac{\text{Number of Unique Subjects with Event during the Risk Period (RP)}}{\text{Sum of Event Exposures for all Subjects (Subject-Years of Exposure)}}$$

The numerator of the IR will include subjects counted only once as soon as they experience a first event during their individual risk period (RP) defined below.

The denominator will be the sum of the times to event for those who experience an event during the risk period and the lengths of risk periods for those who do not experience an event. If a subject experiences multiple instances of the same event, the time to first occurrence of the event will be considered.

In general, a subject is considered at risk to experience an AE while on tofacitinib treatment and within 28 days of stopping tofacitinib treatment. Thus, the risk period extends from the subject's first dose of tofacitinib up to the date of last dose of tofacitinib + 28 days.

For the final analysis, the RP is defined as:

$$\text{RP} = \min(\text{last dose date} + 28 \text{ days}, \text{last contact date}) - \text{first dose date} + 1 \text{ day}.$$

The last contact date will be the maximum of (AE start date, AE stop date, last study visit date, withdrawal date). If a subject is dead, the last contact date will be the death date.

For an interim analysis with a data cutoff date, the RP is defined as:

$$\text{RP} = \min(\text{last dose date} + 28 \text{ days}, \text{last contact date}, \text{data cutoff date}) - \text{first dose date} + 1 \text{ day}.$$

95% CI (corresponding to  $\alpha=0.05$ ) for this IR will be calculated based on the assumption that the actual count of cases (i.e., unique subjects with events) arises from an exact Poisson distribution. The approach used in Daly (1992) describing the calculation of exact confidence limits will be used. If  $x$  denotes the actual number of subjects with events, the (1

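### No contact is scheduled to collect AEs over the 28 days after last dose, and the SAP's last contact rule can then count late events without the matching event-free time

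*Protocol*

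**What the plan says.** Protocol Section 8.2 starts active collection of AEs and SAEs at consent and continues it "through and including a minimum of 28 calendar days after the last administration of the study intervention", or to study completion or withdrawal if that is longer. The same section adds: "Investigators are not obligated to actively seek AEs or SAEs after the participant has concluded study participation".

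The last column of the Schedule of Activities is "End of Study /Early Termination". Section 6.2.5 and Appendix 15 also stop at that visit. Study drug is collected there. If the visit falls within the first 36 months and PK is sampled, Section 6.2.5 has a dose given that day: "The subject's morning dose will be taken at the study site after pre-dose PK sampling". Section 6.2.6 asks for follow-up of unresolved AEs and clinically significant laboratory abnormalities after withdrawal. It does not schedule a contact to ask about new events.

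In SAP Section 6.6, "a subject is considered at risk to experience an AE while on tofacitinib treatment and within 28 days of stopping tofacitinib treatment". For the final analysis the risk period is min(last dose + 28 days, last contact date) − first dose + 1. On the cap, the SAP states: "The last contact date will be the maximum of (AE start date, AE stop date, last study visit date, withdrawal date"). It adds: "If a subject is dead, the last contact date will be the death date".

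On the start of collection, a frequency note to the Schedule of Activities says: "Adverse events (AEs) are captured following the first dose of investigational product". Section 8.2 starts AEs and SAEs alike at consent.

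**The concern.** Safety is the primary objective, and the incidence rates in SAP Section 6.6 are its main quantitative summary. The plan sets a 28-day post-treatment duty and a matching risk window, but gives sites no procedure for meeting the duty. A site can complete every scheduled visit and still not have asked about events up to day 28.

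The SAP rule then makes post-treatment follow-up depend on outcome. If a subject is dosed up to EOS/ET and nothing is reported afterwards, follow-up closes at the visit. If an event is reported afterwards, the risk period is extended to include it. So even if every site phones at day 28, a call that finds nothing leaves no date that the SAP can use. A call that finds an event does. If sites do not phone, late infections, cytopenias, thromboembolic events or pregnancies may not reach the database.

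**Working it through.** **Inputs.** The 28-day window comes from Protocol 8.2 and SAP 6.6, and the risk period (RP) rule from SAP 6.6. Enrolment of about 340 is in Protocol 9.1. Follow-up of about 1 year for A3921165 subjects is in Protocol Section 3 and Appendix 15. Follow-up of 3 and 5 years and event rates of 2 and 10 per 100 subject-years are my assumptions, used to show a range. The documents do not state the size of the post-treatment window in subject-years, so there is no figure of theirs to reproduce.

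**Step 1: apply the SAP rule.** RP = min(last dose + 28, last contact) − first dose + 1, with first dose on day 1.

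| Subject | Last dose | Last contact | RP (days) | Post-treatment days counted |
|---|---|---|---|---|
| Dosed to EOS, nothing reported later | 365 | 365 | 365 | 0 |
| Dosed to EOS, AE starts 10 days later | 365 | 375 | 375 | 10 |
| Dosed to EOS, AE resolves 40 days later | 365 | 405 | 393 | 28 |
| Withdrawal date 14 days after last dose, no AE | 365 | 379 | 379 | 14 |
| Drug stopped 20 days before ET visit, no AE | 345 | 365 | 365 | 20 |
| Tapered off, followed 24 weeks | 197 | 365 | 225 | 28 |

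The first three rows show the dependence on outcome. The last three show that post-treatment time can also count without any AE.

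**Step 2: ceiling on the unscheduled window.** 340 × 28 / 365.25 = 26.1 subject-years. Relative to on-treatment time, 28 / 365.25 = 7.7% at 1 year, 2.6% at 3 years and 1.5% at 5 years.

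**Step 3: effect on a rate.** Take a constant hazard λ per year, T years on treatment ending at the EOS visit, w = 28 / 365.25 = 0.0767 years, and a fraction f of post-visit first events reported. Event-free subjects add no time after the visit. The few days added by subjects with a late event are negligible. The ratio of the SAP rate to the true rate is then about

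1 + f × e^(−λT) × (1 − e^(−λw)) / (1 − e^(−λT)).

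For λ = 0.10, T = 1 and f = 1 this is 1 + 0.9048 × 0.00764 / 0.0952 = 1.073. All results for f = 1:

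| Follow-up | 2 per 100 subject-years | 10 per 100 subject-years |
|---|---|---|
| 1 year | 1.076 | 1.073 |
| 3 years | 1.025 | 1.022 |
| 5 years | 1.015 | 1.012 |

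A simulation of the SAP rule on the same assumptions gave 1.07–1.08, 1.02–1.03 and 1.01. With f = 0.5 at 1 year it gave about 1.04. With f = 0 it gave 1.00: the rate is then unbiased for time up to the visit, and the late events are lost.

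**Step 4: events at stake.** In 26.1 subject-years, a rate of 2 per 100 gives 0.02 × 26.1 = 0.5 expected events, and a rate of 10 per 100 gives 2.6.

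**The case against.** The strongest reply is that the collection duty exists and that the SAP censors in a conventional way. Several parts of it stand.

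- A reader might infer that the 28-day window is not observed at all. The documents do not support that. Section 8.2 requires active elicitation to day 28. Its sentence releasing investigators is most naturally read as covering time after that period, not as cancelling it. Appendix 4 gives subjects tapered off tofacitinib 24 weeks of scheduled visits. Section 7.4.1 expects that some subjects will have stopped drug before the ET visit.
- A reader might infer that post-treatment time enters the rates only through an AE. That is wrong, because visit, withdrawal and death dates also count.
- A reader might infer that every denominator is inflated by 28 days. The cap prevents this. A subject with the event of interest contributes only time to its first occurrence, so a still-open AE adds no days to its own rate; its stop date lengthens follow-up only for other event types.
- The 26 subject-years are a ceiling. The 7–8% applies to follow-up of about one year, which is the A3921165 case. The protocol's change summary for Amendment 7 records planned enrolment rising from about 290 to about 340 when that cohort was added, which suggests about 50 such subjects, or 50 × 28 / 365.25 = 3.8 subject-years. Early entrants may stay longer than a year.
- The study is descriptive. The planned exact Poisson interval for 10 cases runs from 4.8 to 18.4, far wider than this effect.
- EOS need not mean stopping drug. Section 3 and Appendix 15 allow for continued access, with no numbers given.

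None of this supplies a scheduled contact, or a date that would credit an event-free subject with follow-up after EOS/ET.

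**Conclusion.** The concern holds in a limited form. The protocol has a 28-day collection duty with no scheduled contact to carry it out. For subjects dosed up to EOS/ET, the SAP counts a late event if one is reported but gives no post-visit time to subjects without one. It does not apply to subjects who were tapered off, or whose ET visit, withdrawal or death falls well after last dose.

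The overstatement is at most about 7–8% with 1 year of follow-up and 1–3% at 3 to 5 years. This rests on a constant hazard, last dose at EOS/ET for everyone, and full reporting of late events. It would be larger if risk rises after stopping. If late events go unreported there is no overstatement, but they are missing from the safety record. The point is worth fixing because it touches the primary objective and costs little; it does not make the rates unusable.

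The conflict over when AE capture starts is a separate matter. It might be read as another source of bias in these rates, but it is not, since the risk period begins at first dose.

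**What to change.** For subjects still in the study, add one telephone or telehealth contact 28–35 days after last dose, covering AEs, SAEs and pregnancy status, to the Schedule of Activities, Section 6.2.5 and Appendix 15. Record its date in the CRF and add that date to the SAP list that defines last contact date. Appendix 14 already describes AE collection by telehealth, though only for public emergencies. The call would probably reach mainly A3921165 subjects: participation from the other two index studies ends after the first pJIA approval, and Section 1.1 already reports US approval.

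For subjects who have finished, add a sensitivity analysis to SAP Section 6.6 that ends the risk period, for events and person-time alike, at the earlier of last dose + 28 days and the last scheduled visit, with no extension by AE dates. This needs no new data. The main analysis and the planned listing of adjudicated events stay as they are.

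Separately, reconcile the Schedule of Activities note on AE start (first dose) with Section 8.2 (consent).

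The cost is a short amendment, one call per remaining subject, one CRF field, one added date term and one extra table, with a minor demand on site time.
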